### **6.3. Full Analysis Set (FAS) Population**

The full analysis set (FAS) will be defined according to the intention-to-treat (ITT) principle and will consist of all randomised patients who provide consent and receive any amount of the intervention.

The FAS will serve as the primary analysis set. For patients who withdraw consent, data will be used up until the time consent is withdrawn.

#### **6.4. Safety (SAF) Population**

The safety analysis population (SAF) will be identical to the FAS.

For patients who refuse consent only treatment allocation data will be collected and they will not be included in any of the analyses.

#### **6.5. Per-Protocol Set (PPS)**

The per-protocol set (PPS) will exclude all patients in the FAS with major deviations that may have an impact on the primary endpoint (e.g., patients who receive an IMP different to the IMP assigned by randomisation; patients who receive <50% of the planned dose; and patients who significantly violate inclusion/exclusion criteria).

#### **6.6. Subgroup Analysis**

The following subgroups will be analysed: sex (male/female); age group (<65 years/ ≥65 years), race, urgency (elective/non-elective surgery); and complexity (simple/complex surgery [procedures other than isolated ACB, single valve or repair of Atrial Septal Defect (ASD)]). Moreover, the impact of CPB duration on effectiveness will be evaluated by assessing treatment effect based on CPB duration increments (≤120 minutes, 121-180 minutes, >180 minutes).

#### **6.7. Protocol Deviations**

No specific protocol deviations will be considered as this is a randomised, active-control, Phase 3 study.

Classification of protocol deviations as minor and major will be defined a priori. Patients with major protocol deviations that may have an impact on the primary endpoint will be excluded from the per-protocol analyses. The Sponsor and Independent Data and Safety Monitoring Committee (IDSMC) will review the number and nature of major protocol deviations and take appropriate measures to minimise the impact on the study.

A complete listing of protocol deviations (documented as well as derived ones) and the judgement for assessment of patient disposition will be signed before clinical database lock. A description of protocol violations that led to exclusion from any analysis sets will be included in the table part of the Clinical Study Report.

### **7. Statistical Methods**

All statistical analyses will be performed using the SAS® software (Version 9.4 or later).

The analysis of safety will be based on the FAS population.

The primary evaluation of overall efficacy will be performed on the FAS population. In addition, selected efficacy analyses will also be presented for the PPS population.

If not stated otherwise, the following standard descriptive statistics will be presented:

- Descriptive statistics for continuous data

Number (N), mean, standard deviation (SD), min, lower quartile, median, upper quartile and max will be presented. These descriptive statistics will be determined for measured values and optionally for differences to baseline.

- Descriptive statistics for categorical data

Absolute frequencies and percentages will be presented. Percentage bases (denominators) will be identified in the table title or footnote (i.e., all patients at risk, all non-missing cases, all cases). For changes from baseline, shift tables may be generated.

- Exploratory statistics

Although statistical methods are primarily descriptive, two-sided 95% confidence intervals may be presented for selected parameters (e.g., incidences of adverse events) in an exploratory manner.

- Listings

All recorded data will be listed by patient. Identification variable will be the patient ID.

Derived data will be stored in special analysis data sets and will be calculated as outlined in **Appendix 1**.

## 7.1. Conventions

### 7.1.1. Baseline definition

Baseline will be defined as the last value on or prior to the first IMP administration.

### 7.1.2. Missing data

In general, missing data will not be imputed. Due to the nature of the study, important variables are expected to have few missing data. Only for the primary efficacy endpoint in addition to presentation of the primary and secondary endpoints for different analysis sets, multiple imputation methods, may be used to impute missing values.

## 7.2. IMP exposure, compliance

Dose and frequency of IMP administrations of PCC or FP will be summarised in appropriate tables (summary statistics or frequency tables) for the FAS and PPS populations.

### 7.2.1. Medical history

Medical history findings will be coded using the Medical Dictionary for Regulatory Activities (MedDRA) thesaurus in the version current at the time of study start. Coding will be performed by the CRO and agreed upon with the Sponsor before database lock (cf. Data Management Plan [DMP]). The summary tables will display the medical history findings for pre-specified conditions by MedDRA System Organ class (SOC) and Preferred term. Displays will be presented for the FAS and PP populations. Other medical history texts will only be listed.

### 7.3. Prior and concomitant medication

Medications will be coded using the WHO Drug Global thesaurus in the version current at the time of study start. Coding will be performed by the CRO and agreed upon with the Sponsor before database lock (cf. DMP). For concomitant medications, tables will show the frequencies of patients by WHO preferred term. Prior medication will only be listed.

## 7.4. Interim Analysis

An administrative unblinded interim analysis will be carried out when approximately 50% of the target number of evaluable patients have been randomised and treated (100 evaluable patients in each treatment group) by an independent statistician. Unblinded information will be communicated only to the IDSMC. Possible outcomes of this analysis are:

- The study may be stopped for futility after an evaluation of the sample size calculation at the interim analysis.

- The sample size will be re-estimated by the independent statistician.

The study cannot be stopped for efficacy at the interim analysis.

The sample size re-estimation will be based on the evaluation of the conditional power, calculated as described in section 7.3 of [15] making use of the observed response rates and inverse normal combination test statistic with equal weights given by

$$(\Phi^{-1}(1 - p_1) + \Phi^{-1}(1 - p_2))/\sqrt{2},$$

where  $p_1$  and  $p_2$  denote the p-values for testing the non-inferiority null hypothesis for the first and the second stage of the trial, respectively. The aspired conditional power used for the new intended sample size will be 90%.

A 20% dropout rate will be added to the re-estimated sample size of evaluable patients to receive the number of patients to be enrolled in the second stage.

The minimum number of patients for the second stage is 210 evaluable subjects (even if the re-estimated sample size is below this number) or 263 including dropouts. The sample size for the second stage cannot exceed 1250 patients (dropouts included). If the dropout adjusted re-estimated sample size exceeds this threshold, the IDSMC may recommend to either stop the trial for futility or to enrol the maximum number of additional 1250 patients.

## 7.5. Software and analyses

All study data will be transferred to a SAS database (version 9.4 or later) for statistical analysis purposes. Data will be imported from an Electronic Data Capture System via validated SAS programs. If applicable, external data will also be transferred to SAS for presentation of these data in the statistical analyses.

The SAP will be finalised before any unblinded analysis, after agreement with the Sponsor.

## 8. Demographics and Baseline Characteristics

All available demographic data (sex, age, height and body mass index [BMI]) will be summarised in appropriate tables (summary statistics or frequency tables) for the SAF, FAS and PPS populations.

## 9. Evaluation of Treatment Compliance and Exposure

All study treatment will be administered on-site by study-site staff, and all doses are to be documented in the electronic CRF. Administered doses of Octaplex or FP will be recorded for every infusion, including dates, times and batch numbers; the batch numbers will be reported in the final study report. Individual compliance will be derived from these entries and presented as a percentage relative to the recommended dose. Summary statistics for treatment compliance will be displayed.

## 10. Evaluation of Efficacy

### 10.1. Estimand

The components of the estimand are presented in

**Table 1** below.

**Table 1. Description of the primary estimand**

Population	Bleeding cardiac surgery patients with valid informed consent requiring coagulation factor replacement randomized and treated with PCC or FP as defined by in- and exclusion criteria for this study
Endpoint	Haemostatic effectiveness, defined as the absence of any additional haemostatic interventions during the period from 60 minutes to 24 hours after administration of the first treatment

	Yes/No response	
Intercurrent events (ICE)	Event	Strategy
	Discontinuation from study or death	Composite variable strategy: Haemostatic efficacy will be set to 'No', if the patient discontinues for any reason or dies before end of 24-hour period. If discontinuation occurs after the 24-hour period, the response will be considered a valid response.
	Receipt of study medication different from randomisation schedule	Treatment policy strategy: Patients with this ICE will be followed until the end of the 24-hour period and their response will contribute to the analysis as collected and assigned to the randomised treatment group (ITT principle).
	Partial administration of study treatment	Treatment policy strategy: Patients with this ICE will be followed until the end of the 24-hour period and their response will contribute to the analysis as collected.
Population level summary	Difference in proportions of patients with haemostatic effectiveness between the PCC and FP treatment group	

## 10.2. Primary Endpoint

The primary population for the analysis of the efficacy of the IMPs will be the FAS.

The analysis of efficacy will focus on the following primary endpoint:

- P1. Comparison of haemostatic treatment response to *Octaplex* versus FP, defined as 'effective' if no additional haemostatic intervention, such as administration of any systemic haemostatic agents (including platelets, cryoprecipitate, fibrinogen concentrate, activated recombinant factor VII, other coagulation factor products or a second dose of IMP) or any haemostatic interventions (including surgical re-opening for bleeding) is required from 60 minutes to 24 hours after initiation of the first dose of IMP.

The non-inferiority of the primary endpoint 'haemostatic response' will be tested between the treatment groups by means of a one-sided Farrington-Manning score test with non-inferiority margin 0.10 at a significance level of 2.5%, testing the null hypothesis as follows:

$$H_0: p(PCC) \leq p(FP) - 0.10 \text{ will be tested against the alternative } H_1: p(PCC) > p(FP) - 0.10$$

where  $p(PCC)$  and  $p(FP)$  denote the haemostatic response proportions in the PCC and FP treatment groups, respectively.

At the end of the trial, the inverse normal test statistic with equal weights given by

$$(\Phi^{-1}(1 - p_1) + \Phi^{-1}(1 - p_2))/\sqrt{2}$$

is calculated, where  $p_1$  and  $p_2$  denote the p-values for testing the non-inferiority null hypothesis for the first and the second stage of the trial, respectively. If the test statistic exceeds the value 1.96, non-inferiority is demonstrated (see [15]).

Only in case that non-inferiority is demonstrated, i.e., the null hypothesis is rejected at the one-sided 2.5% level of significance, superiority of PCC with regard to the primary endpoint will be investigated:

$H_0: p(\text{PCC}) \leq p(\text{FP})$  will be tested against the alternative  $H_1: p(\text{PCC}) > p(\text{FP})$

The Farrington-Manning score test will be used to calculate a two-sided 95% confidence interval based on the inverse normal test statistic as given above. This confidence interval corresponds with the test decision for showing non-inferiority and/or superiority [16]. This hierarchical test procedure allows to perform the superiority test at the full alpha of 2.5%.

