The study is split in two stages. In the first stage, randomisation (1:1) will continue until 200 evaluable patients are obtained. Then, an administrative unblinded interim analysis will be carried out to re-estimate the sample size or stop for futility (non-binding) if necessary. The sample size in the second stage is limited to 210–800 evaluable patients. Accounting for 20% dropouts, the total sample size of the study will range between 513–1250 if the study is not stopped for futility at the interim.

Subject/Patient Selection Criteria:**Inclusion Criteria:**

1. Adult (≥ 18 years old) patients undergoing any index cardiac surgery employing CPB
2. Coagulation factor replacement with PCC or FP ordered in the operating room for:
 - a. Management of bleeding, or
 - b. Anticipated bleeding in a patient who has been on-pump for >2 hours or has undergone a complex procedure (e.g., aortocoronary bypass [ACB] plus aortic valve replacement)
3. Coagulation factor deficiency, either known to exist (e.g., as indicated by elevated EXTEM clotting time [CT] or INR) or suspected based on the clinical situation
4. Patients who have given written informed consent¹

Exclusion Criteria:

1. Undergoing heart transplantation, insertion or removal of ventricular assist devices (not including intra-aortic balloon pump [IABP]) or repair of thoracoabdominal aneurysm
2. Critical state immediately before surgery with high probability of death within 24 hours of surgery (e.g., acute aortic dissection, cardiac arrest within 24 hours before surgery)

¹ In Canada, informed consent will be obtained after randomisation, in accordance with Article 3.7A of the 2018 Tri-Council Policy Statement on the Ethical Conduct for Research Involving Humans.

Name of Sponsor/Company: Octapharma AG	
Name of Investigational Product: Octaplex	Protocol Identification Code: LEX-211
Name of Active Ingredient: Prothrombin complex concentrate, human	Date of Final Protocol: 25-Aug-2023

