7.2.2.4 Bleeding Data

Severity of bleeding before IMP administration according to the Bleeding Severity Scale by Lewis et al [78] will be collected during surgery.

The comparison of 'major' bleeding based on the universal definition of perioperative bleeding (UDPB) in cardiac surgery [89, 93] (**Table 5**Error! Reference source not found.) will be assessed. The UDPB is a multistage definition for perioperative bleeding based on easily measured clinical endpoints, including total blood loss from chest tubes at 12 hours and 24 hours after chest closure, allogeneic blood components transfused, surgical re-exploration including cardiac tamponade, delayed sternal closure and the need for salvage treatment. Modifications to the UDPB will include addition of fibrinogen concentrate to cryoprecipitate and exclusion of the category of delayed sternal closure.

Depending on these components, bleeding is graded as insignificant, mild, moderate, severe or massive (**Table 5**Error! Reference source not found.) [89].

Intracerebral and gastrointestinal haemorrhages will be documented.

Table 5: Bleeding categories according to the UDPB in adult cardiac surgery (if different categories indicate mixed definitions of bleeding, the worst definition applies) [89]

Bleeding definition	Postoperative chest tube blood loss within 12 h (mL)	RBC (units)	FP (units)	PLT (units)	Fibrinogen concentrate or Cryoprecipitate	PCC	rFVIIa	Re-exploration/tamponade
Class 0 (insignificant)	<600	0	0	0	No	No	No	No
Class 1 (mild)	601–800	1	0	0	No	No	No	No
Class 2 (moderate)	801–1000	2–4	2–4	Yes	Yes	Yes	No	No
Class 3 (severe)	1001–2000	5–10	5–10	N/A	N/A	N/A	No	Yes
Class 4 (massive)	>2000	>10	>10	N/A	N/A	N/A	Yes	N/A

FP, frozen plasma; N/A, not applicable; PCC, prothrombin complex concentrate; PLT, platelets; rFVIIa, activated recombinant factor VII; UDPB, universal definition of perioperative bleeding.

To remove any potential bias from PCC and/or FP dosing, as their use is dictated by the randomisation schedule, a modified version of the UDPB will also be applied, with the following components of the score omitted: administration of PCC and transfusion of FP.

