9.1 Determination of Sample Size

The analysis of the primary efficacy endpoint will involve comparison of haemostatic treatment response to IMP, defined as 'effective' if no additional haemostatic intervention, such as administration of any systemic haemostatic agents (including platelets, cryoprecipitate, fibrinogen concentrate, activated recombinant factor VII, other coagulation factor products or a second dose of IMP) or any haemostatic interventions (including surgical re-opening for bleeding) is required from 60 minutes to 24 hours after initiation of the first dose of IMP.

Patients categorised as having an 'ineffective' haemostatic treatment response to IMP, due to requiring administration of any haemostatic intervention, including a second dose of IMP, in the time window from 60 minutes to 24 hours after initiation of the first IMP dose, will be considered as treatment failures.

Of the more than 100 patients studied in the FARES pilot study, approximately 75% of patients in the PCC group and 65% in the FP group demonstrated haemostatic treatment response from 60 minutes to 24 hours after initiation of the first IMP dose [58]. Using a more conservative estimate of 70% versus 65%, it is estimated that 410 patients will be required to demonstrate non-inferiority with a one-sided α of 0.025, power of $\geq 90\%$ and non-inferiority margin of 0.10 when using a Farrington-Manning score test.

It is anticipated that up to 20% of randomised patients may not meet administration criteria (based on objective Bleeding Severity Scale and INR) due to cessation of haemorrhage between randomisation and delivery of IMP to the operating room and therefore will not receive the therapy.

An administrative unblinded interim analysis will be carried out after 200 evaluable patients have been randomised and treated and will be used to re-estimate the sample size or stop for futility (non-binding) (**Section 9.4**). Patient recruitment will continue during the conduct of the interim analysis. The sample size in the second stage is limited to 210–800 evaluable patients. Accounting for drop-outs as described above, the total sample size will range between 513–1250 if the study is not stopped for futility at the interim (see table below).

	Stage 1	Stage 2 – Minimum	Stage 2 – Maximum	Total - Maximum
Evaluable patients	200	210	800	1000
Sample size including 20% dropouts	250	263	1000	1250

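### The pre-dose Bleeding Severity grade is collected but used in no named SAP analysis: a missed gain in precision and robustness for the primary comparison, not an error in the planned test

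*SAP*

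**What the plan says.** **Collection.** Protocol 7.2.2.4 provides that "Severity of bleeding before IMP administration according to the Bleeding Severity Scale" is collected during surgery, and the flow chart (Table 1) lists a Bleeding Score under surgical data at Visit 2. Protocol section 6 makes at least grade 2 part of the usual condition for giving IMP. The transfusion algorithm (Figure 2 footnotes) also ties the intensity of treatment to the grade.

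**Blinding.** Protocol 3.3.1.6 and section 6 keep operating-room staff blinded until the decision to give IMP is made and the seal is broken.

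**Analysis.** The primary endpoint is "tested between the treatment groups by means of a one-sided Farrington-Manning score test with non-inferiority margin 0.10", applied per stage and combined by the equal-weight inverse normal rule (SAP 10.2). No covariate or stratum enters. The SAP mentions the Bleeding Severity Scale only in the dropout sentence of section 4.2. The grade is absent from:
- the named baseline variables (SAP 8);
- the secondary models (SAP 10.3);
- the sensitivity analyses (SAP 10.4);
- the subgroup list, "The following subgroups will be analysed: sex (male/female); age group" and so on through race, urgency, complexity and bypass duration (SAP 6.6).

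**Size.** "Using a more conservative estimate of 70% versus 65%, it is estimated that 410 patients will be required to demonstrate non-inferiority" (Protocol 9.1). Stage 1 has 200 evaluable patients, and "The sample size in the second stage is limited to 210–800 evaluable patients".

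**The concern.** The endpoint is the need for further haemostatic treatment. How badly the patient was bleeding just before the dose is one of the closest baseline predictors that the trial collects, and the grade-driven algorithm makes a link plausible. It also fits the SAP's baseline definition (last value on or before first IMP, SAP 7.1.1).

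Stratifying a risk-difference test by such a value can leave the risk-difference scale and the 0.10 margin as they are while reducing the variance. It also deals with chance imbalance in severity. Randomisation is stratified by centre only, so such an imbalance can occur, and no named analysis would show or correct it. At stake is a modest amount of power or interval width, and a ready answer if the arms differ in bleeding severity.

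**Working it through.** **1. The plan's own figure.** Inputs (Protocol 9.1): 70% PCC, 65% FP, margin 0.10, one-sided 0.025, power at least 90%, 1:1 allocation. The Farrington-Manning formula with restricted null variance gives 204.4, so 205 per arm and 410 in total. Power at 205 per arm is 90.1%. A simulation of the planned two-stage combination test (100 + 105 per arm) gives 90.2%. The unadjusted test delivers what is promised.

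**2. Effect of adjustment.** With R² the share of outcome variance explained by grade:

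- Unadjusted variance term: 0.70 × 0.30 + 0.65 × 0.35 = 0.4375
- SE = √(0.4375 × (1 − R²)/205)
- Power = Φ(0.15/SE − 1.96), where 0.15 = 0.05 + 0.10

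R² is an assumption, because the documents give neither the grade mix nor response by grade.

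| R² | SE | 0.15/SE | Power | Gain (points) |
|---|---|---|---|---|
| 0 | 0.0462 | 3.247 | 90.1% | 0 |
| 2% | 0.0457 | 3.280 | 90.7% | 0.6 |
| 5% | 0.0450 | 3.331 | 91.5% | 1.4 |
| 10% | 0.0438 | 3.423 | 92.8% | 2.7 |

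The approximate 95% half-width, 1.96 × SE, falls from 9.1 points (R² = 0) to 8.6 points (R² = 10%).

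**3. What such R² values would need.** For a split into grades 3-4 (share s, response a) and grade 2 (response b), R² = s(1 − s)(a − b)²/(p(1 − p)), where p is overall response. Three assumed cases:

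- s = 30%, 57% v 72%: p = 0.675; 0.21 × 0.0225/0.2194 = 2.2%
- s = 35%, 53% v 75%: p = 0.673; 0.2275 × 0.0484/0.2201 = 5.0%
- s = 35%, 47% v 78%: p = 0.6715; 0.2275 × 0.0961/0.2206 = 9.9%

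**4. Inside the planned design.** These three cases were simulated with 100 + 105 per arm, a Mantel-Haenszel risk difference by grade with Wald variance, the equal-weight inverse normal rule and 200,000 runs each. Power is about 90.8%, 91.6% and 92.9%, against 90.1% to 90.2% for the unstratified Wald test. Type I error at the margin is about 2.6%, 2.5% and 2.6% stratified, and 2.5% to 2.6% unstratified.

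**5. If the 5-point advantage is absent.** With both rates at 65% the variance term is 2 × 0.65 × 0.35 = 0.455, and power = Φ(0.10/√(0.455 × (1 − R²)/205) − 1.96). This gives 56.5%, 57.3%, 58.6% and 60.9% for R² of 0, 2%, 5% and 10%.

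**6. Chance imbalance.** The 95% limit for the difference in grade share between arms is 1.96 × √(2s(1 − s)/205). Multiplied by b − a, it shifts the crude difference by 1.3, 2.0 and 2.9 points in the three cases, against a 10-point margin.

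**The case against.** **The planned test is not wrong.** A reader might infer that the trial is underpowered or its primary test unsound. The documents do not support that: 410 reproduces, and the unadjusted difference matches the estimand in SAP 10.1. This objection stands.

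**No patients are saved at the planned size.** A reader might also turn the variance reduction into a smaller trial. The second stage has at least 210 evaluable patients even if re-estimation asks for fewer (SAP 7.4), so the total stays at 200 + 210 = 410 or more. Re-estimation to 90% conditional power, up to 800, already gives some protection. This also stands. A smaller re-estimated second stage is possible only above the floor.

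**The size rests on assumed inputs.** True. The dosing criterion leaves mainly grades 2 to 4, which limits the gain.

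**Recording is not guaranteed.** It is tempting to say that the grade exists for every treated patient and cannot be affected by allocation. The documents schedule collection but promise neither completeness nor an entry before the seal is broken. The visit procedures in Protocol 6.1.3 do not list the score. The flow chart puts it in a visit covering 0 to 24 hours after IMP initiation, and unfinished items may be completed on postoperative day 1, when clinicians are unblinded. A visually judged grade written down late could carry information bias into the primary test. This stands, and it is why late entries must be excluded.

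**Timing.** SAP version 5.0 is dated 28-Oct-2024, with completion planned for the fourth quarter of 2024. The documents do not say whether the interim has been run. Replacing the stage 1 p-value after unblinded data had shaped stage 2 would not be acceptable, so the fix depends on this.

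The separate list of tables (SAP 13) is not available and may include a summary by grade.

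**Conclusion.** The point holds as a missed gain in efficiency and robustness. A plausibly prognostic baseline value is scheduled for collection, is judged before allocation is revealed, and is used in no named SAP analysis. The planned unadjusted test remains valid, with its stated 90% power.

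The gain is nil if grade does not predict response, and about 0.6 to 2.7 power points at 205 per arm if it explains 2% to 10% of outcome variance. It would come as power or a narrower interval, not as fewer than 410 patients. These figures rest on the protocol's 70% versus 65%, on an assumed R², and on grades being recorded before the seal is broken. The documents do not support a claim that a known amount of power is being lost.

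**What to change.** **If no stage 1 data have been unblinded.** In SAP 10.2, compute each stage-wise p-value from a risk-difference score test stratified by pre-IMP grade (3-4 versus 2 or lower), with Mantel-Haenszel weights and the same 0.10 margin. Pooling grades 3 and 4 avoids a sparse grade 4 stratum. Use this test in the same inverse normal combination, in the confidence interval derived from it, and in the conditional-power calculation of SAP 7.4. Keep the unstratified test as the sensitivity analysis in SAP 10.4.

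**If the interim has already been run.** Keep the unadjusted test as primary, and prespecify the stratified test as a supportive analysis before final unblinding.

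**In either case.** Add the grade to the baseline table (SAP 8) and the subgroup list (SAP 6.6). Use only grades recorded before the seal is broken, and assign missing or late grades to a stratum by a rule written in advance.

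**Cost.** SAP wording and modest programming, with no new data item. The main downside is that some grades may be missing or recorded too late to use.
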